10.6.3. Safety

Exposure
Exposure Duration
Duration of exposure to study treatment is calculated as: 
 • treatment stop date – treatment start date +1.

Exposure
Exposure Duration
Exposure Categories

 For the ITT population, the following exposure categories will be derived: ≥1 day, ≥4 weeks, ≥8 weeks, ≥12 weeks, ≥16 weeks, ≥20 weeks and ≥24 weeks

Adverse Events			
AEs of Special Interest			

 AESI have been defined as AEs which have specified areas of interest for FF, VI or UMEC or the overall COPD population. The following table presents the AESI groups. Groups which are not SMQs are made up of a selection of preferred terms (PTs) defined by GSK. The complete list, including the PTs which contribute to each of the groups will be provided by Global Clinical Safety and Pharmacovigilance (GCSP) using the MedDRA version current at the time of reporting. This will be finalized prior to unblinding. 			
AE of special interest group	AE special interest subgroup	Sub-SMQ	
Adrenal suppression			
Anticholinergic syndrome (SMQ)			
Asthma/bronchospasm (SMQ)			
Cardiovascular effects	Cardiac arrhythmia	Arrhythmia related investigations, signs and symptoms (SMQ)	
		Bradyarrhythmia terms, nonspecific (SMQ)	
		Conduction defects (SMQ)	
		Disorders of sinus node function (SMQ)	
		Cardiac arrhythmia terms, nonspecific (SMQ)	
		Supraventricular tachyarrhythmias (SMQ)	
		Tachyarrhythmia terms, nonspecific (SMQ)	
	Ventricular tachyarrhythmias (SMQ)		
		Cardiac failure (SMQ)	
		Ischaemic heart disease (SMQ)	
	Hypertension (SMQ)		
	Central nervous system haemorrhages and cerebrovascular conditions (SMQ)		
Ocular effects	Glaucoma (SMQ)		
	Lens Disorder (SMQ)		
Decreased bone mineral density and associated fractures			
Effects on potassium			
Gastrointestinal obstruction (SMQ)			

Hyperglycaemia/new onset diabetes mellitus (SMQ)		
Hypersensitivity		
Local steroid effects		
Pneumonia		
LRTI excluding pneumonia		
Tremor		
Urinary retention		

Bone Fracture Incidents
 
If a subject suffers fractures in multiple locations with the same date of fracture, this is considered to be one fracture incident.
 
All bone fractures will be reported; and separately by traumatic and non-traumatic bone fractures.

Maximum/Minimum Post-Baseline and Worst-Case Post-Baseline	
Definition	Reporting Details
Maximum post-baseline; (QTcF, QTcB, PR interval, ECG heart rate, pulse rate, systolic BP, diastolic BP and laboratory tests.)	Maximum on-treatment value over all timepoints.
Minimum post-baseline; (Diastolic BP and laboratory tests that do not have a lower limit = 0.)	Minimum on-treatment value over all timepoints.
Worst case post-baseline (ECG findings)	
 • 'Abnormal' if any on-treatment assessment is evaluated as 'Abnormal' • 'Unable to evaluate' if all on-treatment assessments are 'Unable to evaluate' • 'Normal' if any on-treatment assessment is evaluated as 'Normal' and there are no on-treatment assessments evaluated as 'Abnormal'

NOTES :

- The treatment phase definitions specified in Section 10.4.2 will be used and only assessments within the on-treatment period will be considered in assessment of minimum/maximum/worst-case post-baseline.
- Assessment of minimum/maximum/worst-case post-baseline will include data from scheduled, unscheduled and study treatment discontinuation visits (if applicable). Vital signs (heart rate, systolic blood pressure and diastolic blood pressure) collected at an assessment associated with a pneumonia event will also be included in derivation of a 'minimum/maximum post-baseline' assessment.

Laboratory Parameters
 
 • Non-quantifiable laboratory results will be treated as missing in summary displays. However, the results will be listed as received (e.g. '<x' or '>x'). • An 'any visit post-baseline' classification will be derived, in which subjects will be counted in the 'low' and 'high' categories if they reported a low or high value at any scheduled or
--

Laboratory Parameters

unscheduled on-treatment visit during the treatment phase being summarized (see Section 10.4.1 for the definition of treatment phases).
 
 • Change from baseline values will be classified relative to the normal range as ‘to low’, ‘to normal or no change’ or ‘to high’. Subjects who do not change categories or move from out-of-range to normal will be classified as ‘to normal or no change’. • An ‘any visit post-baseline’ change classification will be derived, in which subjects will be counted in the ‘to low’ and ‘to high’ categories if they reported a change from a ‘normal’ baseline to a value below or above the normal range (respectively) at any scheduled or unscheduled on-treatment visit during the treatment phase being summarized (see Section 10.4.1 for the definition of treatment phases). Subjects who did not report a change to a value outside the normal range at any visit after the start of study treatment will be counted in the ‘to normal or no change’ category.
Multiple Measurements for Post-Baseline Visits for Safety

 • Subjects having both High and Low values relative to Normal Ranges at post-baseline visits for safety parameters will be counted in both the High and Low categories of “Any visit post-baseline” row of related summary tables.

ECG			
QTcF and QTcF change from baseline results will be reported in categories as below:			
ECG Parameter	Units	Ranges	
		Lower	Upper
Absolute			
Absolute QTcF Interval	msec	0	≤ 450
		> 450	≤ 480
		> 480	≤ 500
		> 500	≤ 530
		> 530	

ECG			
Change from Baseline			
Change from Baseline QTcF	msec		<-60
		≥-60	<-30
		≥-30	<0
		≥0	< 30
		≥ 30	<60
		≥ 60	

Association of Chest Imaging (X-ray or CT scan) with Pneumonia Event

 A chest X-ray is considered associated with pneumonia if it is performed within -7 to +14 days of the date of onset of pneumonia or the date of resolution, whichever the latter. Pneumonia is considered to be supported by a chest X-ray if there is an associated X-ray which shows the presence of infiltrates. Details of pneumonia events are collected on the Pneumonia Details eCRF page. As there may not be a one-to-one correspondence between these events and pneumonia AESI events, a cross-tabulation will be provided for the association of pneumonia AESI events and those recorded on the Pneumonia Details eCRF page.

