10.7.2. Handling of Missing Data

Element	Reporting Detail
General	
 Missing data occurs when any requested data is not provided, leading to blank fields on the collection instrument : 
 These data will be indicated by the use of a “blank” in subject listing displays. Unless all data for a specific visit are missing in which case the data is excluded from the table. Answers such as “Not applicable” and “Not evaluable” are not considered to be missing data and should be displayed as such. No imputation will be made for any missing numerical data, except in the sensitivity analysis of the primary endpoint to assess the impact of missing data on study results. Missing data will generally not be considered in the calculation of percentages (i.e., the denominator will not include subjects who have missing data at a given time point).
Responder	
 Subjects with a missing baseline will have responder status as missing. Subjects with missing post-baseline data and a subsequent non-missing assessment will not be considered a responder or non-responder but will be left as missing. Subjects with a baseline but all missing post-baseline data will be considered a non-responder at all time points.

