3.30	ITT	Summary of Chemistry Data	SAC
3.31	ITT	Summary of Change from Baseline in Chemistry Data	SAC
3.32	ITT	Summary of Chemistry Data Outside the Normal Range	SAC
3.33	ITT	Summary of Chemistry Changes from Baseline Relative to the Normal Range	SAC
3.34	ITT	Summary of Hematology Data	SAC
3.35	ITT	Summary of Change from Baseline in Hematology Data	SAC
3.36	ITT	Summary of Hematology Data Outside the Normal Range	SAC
3.37	ITT	Summary of Hematology Changes from Baseline Relative to the Normal Range	SAC
Vitals Signs			
3.38	ITT	Summary of Vital Signs	SAC
3.39	ITT	Summary of Change from Baseline Vital Signs	SAC
ECGs			
3.40	ITT	Summary of ECG Values	SAC
3.41	ITT	Summary of Change from Baseline in ECG Values	SAC
3.42	ITT	Summary of QTc(F) (msec) Categories	SAC
3.43	ITT	Summary of Change From Baseline in QTc(F) (msec) Categories	SAC
3.44	ITT	Summary of ECG Findings	SAC
3.45	ITT	Summary of ECG Findings Shifts from Baseline	SAC
3.46	ITT	Summary of ECG Abnormalities	SAC

Safety Tables			
No.	Population	Title	Deliverable
3.47	ITT	Summary of ECG Abnormalities Occurring in at Least 3% of Subjects in Either Treatment Group	SAC

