10.13.8. Safety Figures

Safety : Figures			
No.	Population	Title	Deliverable
Exposure			
3.1	ITT	Plot of Exposure to Study Drug	SAC
Laboratory Parameters			
3.4	ITT	Trellis Display of Maximum Post-baseline Liver Function Test Values, Versus Baseline Liver Function Test Values	SAC
3.5	ITT	Scatter Plots of Maximum Post-baseline Versus Baseline For Chemistry Data	SAC
3.6	ITT	Box Plots of Change from Baseline to Maximum Post-baseline Values for Chemistry Data	SAC
3.7	ITT	Scatter Plots of Minimum Post-baseline Versus Baseline For Chemistry Data	SAC
3.8	ITT	Box Plots of Change from Baseline to Minimum Post-baseline Values for Chemistry Data	SAC
3.9	ITT	Scatter Plots of Maximum Post-baseline Versus Baseline For Hematology Data	SAC
3.10	ITT	Box Plots of Change from Baseline to Maximum Post-baseline Values for Hematology Data	SAC
3.11	ITT	Scatter Plots of Minimum Post-baseline Versus Baseline For Hematology Data	SAC
3.12	ITT	Box Plots of Change from Baseline to Minimum Post-baseline Values for Hematology Data	SAC
12-Lead ECGs			
3.13	ITT	Empirical Distribution Function Plot of Maximum Post-baseline QTcF (msec)	SAC
3.14	ITT	Empirical Distribution Function Plot of Change from Baseline in Maximum Post-baseline QTcF (msec)	SAC

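### SAP 10.6.3 treats bounded laboratory results as missing in summaries, so a `>x` value known to be High is omitted or, in one row, can be counted as no change (minor fix)

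*SAP*

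**What the plan says.** The rule is in SAP 10.6.3, Laboratory Parameters: "Non-quantifiable laboratory results will be treated as missing in summary displays". The next sentence preserves the raw text outside the summaries: "However, the results will be listed as received". Its examples name both directions, and nothing distinguishes a limit inside the normal range from one outside it.

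Four other provisions determine what follows:

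- **Maximum.** SAP 10.6.3 defines the maximum post-baseline laboratory value as "Maximum on-treatment value over all timepoints".
- **Any-visit shift row.** SAP 10.6.3 places in its 'to normal or no change' category "Subjects who did not report a change to a value outside the normal range at any visit after the start of study treatment".
- **Denominators.** SAP 10.7.2 says that, generally, "the denominator will not include subjects who have missing data at a given time point".
- **Imputation.** SAP 10.7.2 also says "No imputation will be made for any missing numerical data, except in the sensitivity analysis of the primary endpoint".

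No convention for substituting or classifying bounded laboratory results appears elsewhere in either document.

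**The concern.** A range table needs only the category of a result, not its exact value. A bounded result often fixes the category, so treating it as missing discards something already known. The loss also depends on the value itself, because at the upper end it is the highest results that are removed.

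Haematology and clinical chemistry are a named safety endpoint under an objective to compare the two regimens (Protocol section 3). The tables and figures are where the arms are set side by side. If the rule is programmed as written, counts of high values can be too low. By-visit percentages for analytes with many `<x` results can be too high.

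**Working it through.** **Inputs.** The documents state no figure for this point, so there is none to reproduce. The rule is traced through SAP 10.6.3, 10.7.2, 10.13.7 and 10.13.8, with the visit schedule from SAP 10.2.

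**1. Displays reached.**

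- Tables: "Summary of Chemistry Data Outside the Normal Range" (Table 3.32), its haematology counterpart 3.36, and the shift tables 3.33 and 3.37.
- Figures: SAP Table 5 lists the laboratory figures under its summary columns, so the rule reaches them too. They include "Scatter Plots of Maximum Post-baseline Versus Baseline For Chemistry Data" (Figure 3.5), and also 3.4, 3.6, 3.9 and 3.10.

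**2. What happens to each kind of result, as written.**

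| On-treatment result | What is known | By-visit range and shift tables | Any-visit shift row, read literally | Maximum figures |
|---|---|---|---|---|
| `>x`, x at or above ULN | High | Not counted as High; generally leaves the denominator | Normal baseline and no other out-of-range value: counted as normal or no change | Cannot supply the maximum |
| `<x`, x at or below ULN | Not High | Generally leaves the denominator | Stays, counted as normal or no change | Cannot supply the maximum |

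The first row is the more serious. In the any-visit shift row the subject is put in the wrong category, not merely omitted. If that row instead drops the subject as missing, the result is still not counted as High. There is a mirror case at the lower end: `<x` with x at or below the lower limit of normal (LLN) is known to be Low.

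**3. How often one result decides the record.** Haematology and biochemistry are scheduled at Screening, Visit 5 and Early Withdrawal only. A subject will often have a single on-treatment value per analyte.

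**4. Illustration, on assumed numbers.** Let N be subjects in an arm with one on-treatment value each, h the number truly High, g those of the h reported as `>x`, and l those reported as `<x` and not High. Then

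reported by-visit percentage = (h − g) / (N − g − l).

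Take N = 1020/2 = 510 (randomisation target, Protocol 9.2.1, ignoring dropout) and assume h = 10. The true value is 10/510 = 1.96%.

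| g | l | Reported |
|---|---|---|
| 2 | 0 | 8/508 = 1.57% |
| 5 | 0 | 5/505 = 0.99% |
| 0 | 51 (10% of 510) | 10/459 = 2.18% |
| 0 | 255 (50% of 510) | 10/255 = 3.92% |
| 2 | 255 | 8/253 = 3.16% |

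In the any-visit shift row read literally, with all baselines normal, the denominator stays at 510: 8/510 = 1.57% for g = 2 and 5/510 = 0.98% for g = 5.

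**5. Effect of `<x` on the comparison of arms.** With g = 0 and a share q of `<x` results, the percentage is multiplied by 1/(1 − q): 1.11 at q = 0.10 and 2.00 at q = 0.50. If q is the same in both arms, the factor cancels in the ratio of the two percentages.

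**The case against.** The strongest case on the other side is that the consequence is unproven and the report has other safeguards.

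- **Frequency.** No assay limits, reportable ranges or rates of bounded results are given. Whether `>x` results arise at all for these analytes cannot be known. This stands.
- **Comparison of arms.** A reader might infer that the comparison is distorted by up to a factor of two. The documents do not support this. The 10% to 50% shares are assumed, the inflation concerns by-visit percentages, and in a randomised double-blind trial there is no stated reason for q to differ by arm. The laboratory displays are descriptive, and SAP 10.10.1 displays no treatment p-values.
- **Severe values elsewhere.** A reader might also infer that extreme values vanish from the report. They do not. The raw text goes to listings. Clinically significant abnormalities can be adverse events, with an exception for those associated with the underlying disease (Protocol 12.4.1). Defined combinations of liver findings are serious adverse events (Protocol 12.4.2), and liver events have Listings 42 to 47. One caveat is that Listings 16 and 17 cover only subjects with an out-of-range value, and the SAP does not say whether a bounded result alone qualifies.
- **Repeat tests.** Unscheduled on-treatment values count towards maxima and any-visit rows, and Protocol 7.4.6 calls for repeats of clinically significant abnormal results. It is therefore too strong to say that one bounded value normally removes the whole post-baseline record. The relief is limited at Week 24, because SAP 10.4.2 ends the on-treatment phase one day after the treatment stop date.
- **Tables or figures.** Laboratory maxima are planned only as figures, so no table of maxima is affected.

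None of this answers the central point: the rule, as written, does not count as High a result known to be High.

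**Conclusion.** The point holds as a minor defect in safety reporting. The SAP's stated rule omits known-High `>x` results from the by-visit range and shift tables and from the maximum figures. On the literal wording of the any-visit shift row, it can also misclassify them as normal or unchanged. The `<x` results known not to be High generally drop out of by-visit denominators, which pushes the percentage High the other way.

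The size is unknown and may be small. The percentages above rest on assumed counts, 510 subjects per arm and one on-treatment value each; they show direction only. The defect is confined to summary displays and does not touch the primary endpoint or any inferential result. The documents support neither a loss of severe values from the report as a whole nor a bias between arms.

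**What to change.** Replace the sentence in SAP 10.6.3 with wording such as:

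*In range-classification and shift summaries, results reported as `<x` or `>x` are classified against the normal range using x wherever x determines the category (`>x` with x at or above ULN is High; `<x` with x at or below LLN is Low; `<x` with x at or below ULN is not High) and stay in the denominator. Where x does not determine the category, the result is shown as indeterminate. In maximum/minimum and change-to-maximum/minimum displays, x is used as the value and flagged as a bound. Means exclude such results, with the number excluded shown.*

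The indeterminate class is needed for cases such as `>x` with x below ULN. The provision for change is needed because box plots of change to maximum and minimum are planned (Figures 3.6, 3.8, 3.10 and 3.12).

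The cost is a short SAP edit and minor programming, with no protocol change. The downside is that some displayed extremes and changes will be bounds, not exact values.

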- Demography may be captured at either the Pre-screen Visit or Screening Visit (for subjects who do not have a Pre-screen Visit).
- The IRT will be used for randomisation, emergency unblinding and study treatment supply management (Please refer RAMOS NG IRT manual for more information)
- At Screening Visit 1 both pre and post-bronchodilator spirometry will be conducted. Pre-bronchodilator spirometry will be performed prior to the subject taking their morning dose of their usual COPD treatment, between 6am and 11am and after withholding rescue albuterol/salbutamol for ≥4 hours.
- At Visits 2-5 (and the Early Withdrawal Visit), pre-bronchodilator spirometry will be performed prior to taking the morning dose of study treatment, between 6am and 11am and after withholding rescue albuterol/salbutamol for ≥4 hours.

- g. Patient reported assessments should be conducted in the following order and before other study assessments: SGRQ-C, BDI/TDI.
- h. Close out eDevice for any subject who fails to randomize, withdraws early, or completes Visit 5.
- i. Physical examination may include height, weight, blood pressure, temperature, heart rate.
- j. Vital signs must be performed prior to spirometry and prior to taking morning dose of study medication.
- k. ECG to be obtained 15 - 45 minutes post-dose at treatment Visit 5 and Early Withdrawal Visit (if possible). If a subject is not dosed at Early Withdrawal, then an ECG can be taken at any time during the visit
- l. Chest X-ray (PA and lateral) is required at Screening (or historical x-ray obtained within 3 months prior to Screening) and at anytime there is a suspected pneumonia or a mod/severe exacerbation.
- m. Pulse oximetry must be performed at V2 and anytime there is a suspected pneumonia or a moderate or severe exacerbation.
- n. PK subset A: PK samples of 120 subjects at selected sites, to be obtained at two time points at Visit 4: pre-dose and in the window 5 to 15 minutes post-dose.
PK subset B: PK samples of 60 subjects at selected sites, to be obtained and Visit 4: pre-dose, 5-15min, 45-90min, 2.5-4h, 6-8h, 10-12h, 23-24h post-dose.
- o. PK subset A: PK samples of 120 subjects at selected sites, to be obtained at two time points at Visit 5: 5 to 15 minutes post-dose and 45 to 90 minutes post-dose.
- p. The genetics blood sample should be taken at V5 or at any visit after Randomisation (V2).
- q. Haematology and chemistry panels will include liver chemistry, and potassium and glucose levels.

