7.4.9. Pneumonia

All suspected pneumonias will require confirmation as defined by the presence of new infiltrate(s) on chest x-ray AND at least 2 of the following signs and symptoms:

- Increased cough
- Increased sputum purulence (colour) or production
- Auscultatory findings of adventitious sounds (*e.g.* egophony, bronchial breath sounds, rales, etc.)
- Dyspnoea or tachypnoea
- Fever (oral temperature > 37.5 °C)
- Elevated WBC (>10,000/mm³ or >15% immature forms)
- Hypoxemia (HbO₂ saturation ≤88% or at least 2% lower than baseline value)

All pneumonias must be captured on the AE/SAE page of the eCRF and on the pneumonia page of the eCRF.

The investigators and site staff should remain vigilant for the possible development of pneumonia in patients with COPD as the clinical features of such infections overlap with the symptoms of COPD exacerbations. For all suspected cases of pneumonia, investigators are strongly encouraged to confirm the diagnosis (this includes obtaining a chest x-ray-) and to initiate appropriate therapy as promptly as possible. All diagnoses of pneumonia (radiographically confirmed or unconfirmed) must be reported as an AE or SAE (if applicable).

Note: Pulse oximetry should be measured at any time a moderate or severe exacerbation is reported or pneumonia is suspected and recorded in the source documents and on the pneumonia page of the eCRF if applicable.

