7.4.11. Radiography (Chest X-Rays)

Confirmation by chest x-ray (posteroanterior and lateral) should be performed as soon as possible and preferably within 48 hours of suspected pneumonia and/or moderate or severe exacerbation. All chest x-rays will be reviewed by the investigator to confirm the presence of new radiographic findings compatible with pneumonia. In all cases, the signs and symptoms that were used to identify the pneumonia must be documented in the source documents and eCRF. Diagnoses of pneumonia must be recorded as adverse events in the eCRF.

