8.2.1.2. Pneumonia

Summaries of pneumonia will include data from the Pneumonia Details CRF form.

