
 • Each COPD exacerbation will be categorized based on severity as follows: 
 ○ Mild: no treatment with systemic/oral corticosteroids and/or antibiotics and no hospitalization ○ Moderate: required treatment with systemic/oral corticosteroids and/or antibiotics (not involving hospitalization) ○ Severe: required in-patient hospitalization • The duration of the exacerbation will be calculated as (exacerbation resolution date or date of death - exacerbation onset date + 1). • The time to the first on-treatment exacerbation will be calculated as (exacerbation onset date of first on-treatment exacerbation – date of start of treatment + 1). • Subjects will be represented from their Week 0 date to the earliest of the event or censoring. For subjects who do not experience the event will be censored at the earliest of the date of their treatment stop date +1 day or the date of death.
Association to Chest Imaging (X-ray or CT Scan)

 • A chest X-ray or CT scan is considered associated with a moderate/severe exacerbation if it is performed within 0 to +14 days of the exacerbation start date.

SAC BDI/TDI
General

 • The BDI focal score will be calculated as the sum of the ratings recorded for each of the three individual scales (Functional Impairment, Magnitude of Task, Magnitude of Effort). Each of these scales has five possible scores ranging from 0 to 4 (with lower scores indicating more impairment), so the range of the BDI focal score is 0 to 12. If a score is missing for any of the three scales, then the BDI focal score will be set to missing. BDI is assessed at baseline (Week 0). • The SAC TDI focal score will be calculated as the sum of the ratings recorded for each of the three individual scales (Functional Impairment, Magnitude of Task, Magnitude of Effort). Each of these scales has a possible score ranging from -6 to +6. SAC TDI focal score is calculated as the sum of the three individual scores and then divided by 2 (so the range of the TDI focal score is -9 to +9). If a score is missing for any of the three scales, then the SAC TDI focal score will be set to missing. • If the language of the SAC TDI conducted at a visit is different to the language for the BDI, all TDI scores at that visit and all subsequent visits will be set to missing
Responder Status according to SAC TDI Focal Score

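### Read plainly, the SAP links chest X-rays to a pneumonia by its resolution date, so the diagnostic film of a longer event can fall outside the window and the event be classed as not X-ray supported

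*SAP*

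**What the plan says.** SAP section 10.6.3, under the association of chest imaging with pneumonia, counts an X-ray as associated if it was performed "within -7 to +14 days of the date of onset of pneumonia or the date of resolution, whichever the latter". The next rule depends on it: "Pneumonia is considered to be supported by a chest X-ray if there is an associated X-ray which shows the presence of infiltrates".

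The protocol ties the film to suspicion. Section 7.4.11 says that confirmation by X-ray "should be performed as soon as possible and preferably within 48 hours of suspected pneumonia and/or moderate or severe exacerbation". Footnote l of the Time and Events Table (section 7.1) requires a film at Screening and "at anytime there is a suspected pneumonia or a mod/severe exacerbation". No film is scheduled at resolution. Section 7.4.9 gives the early film its role: "All suspected pneumonias will require confirmation as defined by the presence of new infiltrate(s) on chest x-ray", together with at least two listed signs or symptoms.

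For exacerbations, which carry the same 48-hour request, SAP section 10.6.4 anchors imaging on the start of the event: "within 0 to +14 days of the exacerbation start date".

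SAP section 10.7.2.1 imputes a partial pneumonia stop date to the last day of the month, and to December if the month is unknown.

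**The concern.** The film that matters for a pneumonia is taken when it is suspected. A window centred on resolution moves away from that film as the event gets longer. A pneumonia with an infiltrate on a prompt film, exactly as the protocol asks, could then be reported as lacking X-ray support.

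Protocol section 4.6.3 names pneumonia as a key risk of ICS-containing treatment, so a reader of the safety report is likely to look at radiographic support. The wording also allows two readings that classify the same film differently. Two programmers could produce different counts from the same data, which a prespecified derivation should prevent.

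**Working it through.** The plan states no count to reproduce, so the check is date arithmetic on the rule.

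**Inputs**
- Window of -7 to +14 days around the later of onset and resolution: SAP 10.6.3.
- Diagnostic film at onset day 0 to +2: from the 48-hour preference in Protocol 7.4.11, taking suspicion as onset (an assumption).
- Duration D, in days from onset to resolution: not given in either document. Values from 5 to 28 are used for illustration.

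**Plain reading.** D is never negative, so the later date is resolution whenever it is known. A film on day f after onset is associated if D - 7 ≤ f ≤ D + 14. It falls before the window when D > f + 7:
- f = 0: lost when D is 8 or more.
- f = 1: lost when D is 9 or more.
- f = 2: lost when D is 10 or more.

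**Second reading.** The film is associated if -7 ≤ f ≤ max(14, D). Films on days 0 to +2 always satisfy this.

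| D (days) | Plain reading: window from onset | Day 0 film | Day +1 film | Day +2 film | Second reading: window from onset |
|---|---|---|---|---|---|
| 5 | -2 to +19 | in | in | in | -7 to +14 |
| 7 | 0 to +21 | in | in | in | -7 to +14 |
| 8 | +1 to +22 | out | in | in | -7 to +14 |
| 9 | +2 to +23 | out | out | in | -7 to +14 |
| 10 | +3 to +24 | out | out | out | -7 to +14 |
| 14 | +7 to +28 | out | out | out | -7 to +14 |
| 21 | +14 to +35 | out | out | out | -7 to +21 |
| 28 | +21 to +42 | out | out | out | -7 to +28 |

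The readings differ at both ends. For a 21-day event the upper limit is day 35 on one and day 21 on the other.

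**Partial stop dates.** Suppose onset and film are on the 3rd, and the event resolves later that month with the day missing. The stop date is imputed to the 28th to 31st, depending on the month. Subtracting 7 days, the plain-reading window opens on the 21st to 24th. Even a short pneumonia then loses its film. A completely missing resolution date is not imputed, so onset would presumably serve as the anchor, though the SAP does not say so.

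**The case against.** The strongest reply is that the sentence was probably meant to run from 7 days before onset to the later of onset plus 14 days and resolution. If the anchor were simply the later date, naming onset would be redundant for every resolved event. This reading is tenable and may be the intended one. It is not what the text states, so it supports rewording the rule rather than leaving it.

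The second reply concerns reach, and it stands. Several stronger conclusions are tempting but unsupported:

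- *Pneumonia would be under-counted.* It would not. SAP section 8.2.1.2 says "Summaries of pneumonia will include data from the Pneumonia Details CRF form", with no X-ray condition, and the AESI groups in section 10.6.3 are built from coded adverse event terms.
- *Confirmed and unconfirmed cases would be mixed up.* Confirmation is defined in Protocol 7.4.9, and the investigator reviews the films under 7.4.11. Neither uses the SAP window.
- *The primary analysis is touched.* Under SAP 10.1.2, FEV1 data are removed from the onset of a pneumonia, whether or not a film supports it.
- *Most events would be affected.* Protocol 12.7.1.4 gives antibiotic courses of 7 to 14 days, but that is treatment time in guidance on exacerbations. It does not show how long pneumonias last from onset to resolution.
- *The comparison is biased.* Both arms receive the same FF dose under blinding and the same rule applies to both. The documents show no mechanism for a differential effect.

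An event also loses its support only if no other film with infiltrates falls in the late window. Films and pneumonia data are listed by subject (Listings 39 and 41), so none disappears from the report.

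**Conclusion.** The point holds as a defect of wording in a descriptive derivation. On the plain reading, a prompt diagnostic film drops out of the window once resolution is 8 to 10 or more days after onset, depending on whether the film was taken on day 0, +1 or +2. Imputed stop dates move the window later still. The direction for films taken at onset is clear: longer events lose support.

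The conclusion rests on three assumptions: suspicion coincides with onset, a resolution date is recorded or imputed, and the programmer follows the plain reading. The share of events affected cannot be computed from the documents.

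The effect stops at the X-ray support classification. No title in the SAP's list of displays names that classification; the pneumonia detail tables (3.23 and 3.25) are its likely place. It is worth correcting because it describes a key risk and the correction is almost free, but no endpoint or main safety count depends on it.

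**What to change.** Replace the sentence in SAP 10.6.3 with one that states each limit separately, for example:

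*A chest X-ray or CT scan is associated with a pneumonia if its date is on or after (onset date - 7 days) and on or before the later of (onset date + 14 days) and (resolution date).*

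Add that the upper limit is onset + 14 days when no resolution date is available. With this wording, films on days 0 to +2 are associated at every duration, and an imputed stop date can only extend the upper limit. If the sponsor prefers resolution + 14 days as the upper limit, the text should say so explicitly. CT is included because the heading of the rule covers it although the pneumonia sentence names only X-ray.

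The cost is one sentence in the SAP and the matching line in the dataset specification. No data collection changes.
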